## 3.5 Suspension or Early Termination of the Clinical Investigation

## Clinical Investigation Plan

The Sponsor reserves the right to discontinue the clinical investigation at any stage or reduce the follow-up period with suitable written notice to the investigator. Possible reason(s) may include, but are not limited to:

- Unanticipated adverse device effect (e.g., UADE) occurs and it presents an unreasonable risk to the participating subjects
- Steering committee makes a recommendation to stop or terminate the clinical investigation (such as higher frequency of anticipated adverse device effects)
- Further product development is cancelled

Should the clinical investigation be discontinued by the Sponsor, subjects will be followed per routine hospital practice with device-related AEs reported to the Sponsor as per vigilance/commercial reporting requirements.

Should this occur, the investigator shall return all clinical investigation materials (including devices) to the Sponsor, and provide a written statement as to why the premature termination has taken place to the EC (if applicable). All applicable clinical investigation documents shall be subject to the same retention policy as detailed in [Section 11.5] of the CIP.

A Principal Investigator, EC or regulatory authority may suspend or prematurely terminate participation in a clinical investigation at the investigational sites for which they are responsible. The investigators will follow the requirements specified in the Clinical Trial Agreement.

If the Sponsor suspends or prematurely terminates the clinical investigation at an individual site in the interest of safety, the Sponsor will inform all other Principal Investigators.

If suspension or premature termination occurs, the Sponsor will remain responsible for providing resources to fulfill the obligations from the CIP and existing agreements for following the subjects enrolled in the clinical investigation, and the Principal Investigator or authorized designee will promptly inform the enrolled subjects at his/her site, if appropriate.

## 4 ENDPOINTS

### 4.1 Primary Endpoint and Rationale

The primary safety endpoint of the FlexNav EU study is VARC-2 defined major vascular complications at 30 days post index procedure.

According to VARC-2 criteria, a major vascular complication is defined as:

- Any aortic dissection, aortic rupture, annulus rupture, left ventricle perforation, or new apical aneurysm/pseudo-aneurysm or
- Access site or access-related vascular injury (dissection, stenosis, perforation, rupture, arterio-venous fistula, pseudoaneurysm, hematoma, irreversible nerve injury, compartment syndrome, percutaneous closure device failure) leading to death, life-threatening or major bleeding\*, visceral ischemia or neurological impairment or
- Distal embolization (non-cerebral) from a vascular source requiring surgery or resulting in amputation or irreversible end-organ damage or
- The use of unplanned endovascular or surgical intervention associated with death, major bleeding, visceral ischemia or neurological impairment or

## Clinical Investigation Plan

- Any new ipsilateral lower extremity ischemia documented by patient symptoms, physical exam, and/or decreased or absent blood flow on lower extremity angiogram or
- Surgery for access site-related nerve injury or
- Permanent access site-related nerve injury

### 4.2 Descriptive Endpoint(s)

A selection of descriptive endpoints including valve performance parameters, clinical function assessments and adverse events defined according to VARC 2 criteria will be assessed at 30 days and at 12 months as defined below. All descriptive endpoints will be summarized separately using descriptive statistics.

Descriptive endpoints to be assessed at 30 days and included in the CE Mark submission:

- Non-hierarchical composite of all-cause mortality, disabling stroke, life threatening bleeding requiring blood transfusion, acute kidney injury requiring dialysis, or major vascular complications at 30 days from the index procedure.
- All-cause mortality at 30 days from the index procedure.
- Disabling stroke at 30 days from the index procedure.
- Non-disabling stroke at 30 days from the index procedure.
- Life threatening bleeding requiring blood transfusion at 30 days from the index procedure.
- Major bleeding at 30 days from the index procedure.
- Acute kidney injury at 30 days from the index procedure.
- Minor vascular complication rates at 30 days from the index procedure.
- Permanent pacemaker insertion at 30 days from the index procedure.
- Paravalvular Leak (PVL) at 30 days from the index procedure.
- NYHA functional classification at 30 days from the index procedure.
- KCCQ Quality of Life (QOL) score from baseline to 30 days from the index procedure.
- Technical device success defined as successful vascular access, delivery and deployment of the Portico Valve; retrieval with the delivery system and correct positioning of a single valve in the proper anatomical location.

Additional descriptive endpoints to be assessed at one year but not included in the CE Mark submission:

- Composite of all-cause mortality or disabling stroke at one year from the index procedure.
- All-cause mortality at one year from the index procedure.
- Disabling stroke at one year from the index procedure.

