### 3.4.4 Adjudication of Adverse Events by an Independent Clinical Events Committee

An independent Clinical Events Committee (CEC), consisting of, at a minimum, an interventional cardiologist, cardiologist, cardiothoracic surgeon, and a neurologist will review and adjudicate pre-specified events reported by investigators or identified by Safety personnel in the clinical investigation as defined in the CEC Manual of Operations Charter. Events related to primary and descriptive endpoint criteria will be adjudicated according to the Valve Academic Research Consortium (VARC-2) definitions. The CEC will have final adjudication responsibilities for subject outcomes related to primary and descriptive outcome measures.

The same CEC used in the Portico US IDE pivotal trial will be utilized for this clinical investigation.

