## Clinical Investigation Plan

with use of the FlexNav™ Delivery System will be similar to those associated with any routine TAVI procedure and related follow-up.

As outlined in the IFU, potential anticipated adverse events associated with the use of transcatheter bioprosthetic heart valves include but are not limited to, the following:

1. access site complications (e.g., pain, bleeding, infection, hematoma, pseudoaneurysm, etc.)
2. acute coronary obstruction
3. acute myocardial infarction
4. allergic reaction to antiplatelet agents, contrast medium, or valve components
5. aortic rupture
6. ascending aorta trauma
7. atrio-ventricular node block
8. cardiac arrhythmias
9. embolism
10. endocarditis
11. heart failure
12. hemodynamic compromise
13. hemolysis
14. hemolytic anemia
15. hemorrhage
16. hypotension or hypertension
17. infection
18. myocardial ischemia
19. mitral valve insufficiency
20. multi-organ failure
21. non-structural dysfunction (i.e., entrapment by pannus, paravalvular leak, inappropriate sizing or positioning)
22. pericardial effusion
23. perforation of the myocardium or a blood vessel
24. pannus
25. renal insufficiency or renal failure
26. sepsis
27. stroke
28. structural deterioration (i.e., calcification, leaflet tear)
29. thrombosis
30. tamponade
31. valve migration
32. vessel dissection or spasm.

It is possible these complications could lead to:

1. transfusion
2. conversion to open surgical procedure
3. reoperation
4. emergent balloon valvuloplasty
5. emergent percutaneous coronary intervention (PCI)
6. emergent surgery (i.e., coronary artery bypass, heart valve replacement)
7. explantation
8. permanent disability

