### Bleeding (VARC 2)

Life-threatening or disabling bleeding

- Fatal bleeding (BARC type 5) **OR**
- Bleeding in a critical organ, such as intracranial, intraspinal, intraocular, or pericardial necessitating pericardiocentesis, or intramuscular with compartment syndrome (BARC type 3b and 3c) **OR**
- Bleeding causing hypovolemic shock or severe hypotension requiring vasopressors or surgery (BARC type 3b) **OR**
- Overt source of bleeding with drop in hemoglobin of greater than or equal to ( $\geq$ ) 5 g/dl or whole blood or packed red blood cells (RBCs) transfusion greater than or equal to ( $\geq$ ) 4 U (BARC type 3b). *Given 1 U of packed RBC typically will raise blood hemoglobin concentration by 1 g/dl, an estimated decrease in hemoglobin will be calculated.*

Major bleeding (BARC type 3a)

- Overt bleeding either associated with a drop in the hemoglobin level of at least 3.0 g/dl or requiring transfusion of two or three units of whole blood/ RBC, or causing hospitalization or permanent injury, or requiring surgery **AND**
- Does not meet criteria of life-threatening or disabling bleeding

Minor bleeding (BARC type 2 or 3a, depending on the severity)

- Any bleeding worthy of clinical mention (e.g., access site hematoma) that does not qualify as life-threatening, disabling or major

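### A life-threatening bleed that is not transfused falls into neither 30-day bleeding endpoint, while a milder 3 g/dl haemoglobin drop is counted

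*Protocol*

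**What the plan says.** Protocol 4.2 lists the 30-day descriptive endpoints for the CE Mark submission and says that its adverse event endpoints follow VARC-2. Two of them are bleeding rates: "Life threatening bleeding requiring blood transfusion at 30 days from the index procedure", and major bleeding over the same period. The composite repeats the transfusion condition: "Non-hierarchical composite of all-cause mortality, disabling stroke, life threatening bleeding requiring blood transfusion, acute kidney injury requiring dialysis, or major vascular complications". SAP 1.4.2 carries the same wording and adds no unrestricted bleeding row.

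Appendix II of the protocol, under Bleeding (VARC 2), defines life-threatening or disabling bleeding by a list joined by OR:

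- fatal bleeding;
- bleeding in a critical organ, including a pericardial bleed that needs pericardiocentesis;
- bleeding that causes hypovolaemic shock, or severe hypotension treated with vasopressors or surgery;
- "Overt source of bleeding with drop in hemoglobin of greater than or equal to" 5 g/dl, or transfusion of at least 4 units.

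Major bleeding includes overt bleeding "associated with a drop in the hemoglobin level of at least 3.0 g/dl", subject to a second condition: "Does not meet criteria of life-threatening or disabling bleeding".

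**The concern.** The endpoint list narrows the top grade of bleeding to transfused cases, but the grade below still excludes everything that belongs in the top grade. Bleeds that are severe enough for the top grade but were not transfused have no bleeding row.

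The two named rates then do not nest by severity: a worse bleed can disappear from both rows while a milder one is shown. A reader who adds the rows to obtain all serious bleeding under the protocol's own definition can get too low a figure. This matters because characterising safety is the study's only primary objective, and Protocol 1.1.1.2 itself links vascular and bleeding complications to higher morbidity and mortality.

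**Working it through.** This is a check of definitions. Each kind of bleed in Appendix II is assigned to the endpoints in Protocol 4.2, taking the subject as not transfused.

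| Bleed, no transfusion | Life-threatening, transfused row | Major bleeding row | 30-day composite |
|---|---|---|---|
| Overt, drop of 3.0 to below 5 g/dl, no life-threatening feature | No | **Yes** | Only through another component |
| Overt, drop of 5 g/dl or more | No | No (excluded as too severe) | Only through another component |
| Shock or severe hypotension treated with vasopressors or surgery | No | No | Only through another component |
| Non-fatal pericardial bleed, drained | No | No | Only through another component |
| Intracranial bleed | No | No | If it is a disabling stroke or fatal |
| Fatal bleed | No | No | Yes, as a death |
| Life-threatening bleed from access-related vascular injury | No | No | Yes, as a major vascular complication |

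The last row follows from Protocol 4.1, which counts access-related injury "leading to death, life-threatening or major bleeding" with no transfusion condition. Aortic rupture, annulus rupture and left ventricle perforation also enter the composite that way. The gap in the composite is therefore limited to untransfused life-threatening bleeds that meet no other component.

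Such a case is foreseeable. Protocol 15.2.1 lists "perforation of the myocardium or a blood vessel" and tamponade among the anticipated events, whereas the major vascular definition names only the left ventricle. A drained, untransfused, non-fatal pericardial bleed from a perforation elsewhere in the heart can miss both bleeding rows and the composite.

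**Illustration of size.** The documents give no bleeding rate, so the number of missed events cannot be estimated. The effect of one uncounted event on a displayed rate can be shown with the exact 95% Clopper-Pearson interval of SAP 2.2.2, at n = 73 (the minimum for the primary analysis) and n = 200 (the maximum enrolment).

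- With 0 events, the upper limit is 1 − 0.025^(1/n).
- With 1 event, the lower limit is 1 − 0.975^(1/n), and the upper limit is the 97.5th percentile of a Beta(2, n − 1) distribution.

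| n | Reported with 0 events | With 1 event |
|---|---|---|
| 73 | 0.00% (0.00 to 4.93) | 1/73 = 1.37% (0.03 to 7.40) |
| 200 | 0.00% (0.00 to 1.83) | 1/200 = 0.50% (0.01 to 2.75) |

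One event is thus worth 1.4 percentage points at n = 73 and 0.5 points at n = 200.

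**The case against.** The literal gap is hard to dispute. The case on the other side is that it is small and has little consequence.

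- **The rows are not meant to be added.** Protocol 4.2 says that the descriptive endpoints are summarised separately, and the visible text attaches no hypothesis or success rule to them. This is true and limits the harm, but each row still has to be read against the VARC-2 grade it is named after, and the severity inversion remains.
- **The events are reported elsewhere.** SAP 3.2 tabulates all adjudicated adverse events. Part of that section is redacted, and the table mock-ups are not in the documents, so a separate life-threatening row might exist. That cannot be ruled out, but it cannot be assumed either, and general adverse event tables are not the named endpoints.
- **Other routes narrow the gap.** Haemorrhagic strokes have their own stroke rows, and a disabling one enters the composite. Unplanned surgery associated with major bleeding is a major vascular criterion, although its wording does not mention life-threatening bleeding. These routes lead through other endpoints or components and do not put the bleed into a bleeding row.
- **The haemoglobin estimate allows for transfused units.** If so, some drops of 5 g/dl or more will be in transfused subjects. That does not help the untransfused.
- **The restriction looks deliberate.** It is worded alike in both documents, and Protocol 3.2 aligns key data collection with the US IDE FlexNav study so that 30-day data can be pooled. The visible text does not give this as the reason. If it is the reason, it argues for keeping the restricted row, not against adding an unrestricted one.

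What stands is that the number of affected subjects may be small, and that the 0/73 versus 1/73 comparison would look the same for any single uncounted event.

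**Conclusion.** The concern holds. Under the visible definitions, an untransfused life-threatening bleed is counted in neither 30-day bleeding endpoint, although a smaller haemoglobin drop is counted as major bleeding. It reaches the composite only by also meeting another component.

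The conclusion rests on reading the words about transfusion as a real restriction, which both documents support by repeating them, and on applying Appendix II as written. The size is unknown. The effect on the primary endpoint is none. This is a reporting inconsistency that should be corrected because the correction is cheap; it does not threaten the study's main conclusion.

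**What to change.** In Protocol 4.2 and SAP 1.4.2:

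1. Add a 30-day endpoint: *VARC-2 life-threatening or disabling bleeding, whether or not transfused*.
2. Keep the existing transfusion-restricted endpoint directly beneath it, labelled as a subset.
3. Keep the existing composite, and report it a second time with the unrestricted bleeding component.

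Because the restricted endpoint and the existing composite stay as they are, any pooling with the US IDE FlexNav study is untouched.

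The cost is two extra table rows. Protocol 3.4.4 already provides that "Events related to primary and descriptive endpoint criteria will be adjudicated according to the Valve Academic Research Consortium (VARC-2) definitions", and grading a bleed as major already requires the committee to test the life-threatening criteria, so no new data are needed. The reported bleeding and composite rates may come out slightly higher.

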## Clinical Investigation Plan

- Non-disabling stroke at one year from the index procedure.
- Paravalvular Leak (PVL) at one year from the index procedure.
- KCCQ Quality of Life (QOL) score from baseline and one year from the index procedure.
- NYHA functional classification at one year from the index procedure.

## 5 SUBJECT SELECTION AND WITHDRAWAL

### 5.1 Subject Population

This clinical investigation will enroll male and female subjects from a valvular disease population who have symptomatic, severe AS and are determined to be at high or extreme operative risk for SAVR.

Subjects must sign and date the informed consent prior to conducting any study-specific procedures not considered standard of care. Any patient data transmitted to the independent CT and Echocardiographic core laboratories, SSC or Sponsor for screening purposes must have prior signed and dated Informed Consent.

The operative risk determination of study candidates will be based on the Society of Thoracic Surgeons (STS) Adult Cardiac Surgery Risk Calculator score and the EuroSCORE II score.

Subject case review will be conducted by the SSC to determine the patient's anatomical eligibility to receive a Portico valve using the FlexNav™ Delivery System and final risk classification. Refer to the SSC charter for a full description of the review process. Subjects will be assigned as high or extreme risk according to criteria below:

#### 5.1.1 High Risk Classification:

High risk classification will be assigned to subjects with severe aortic stenosis symptoms for whom conventional aortic valve replacement surgery is associated with high risk equivalent to an STS risk score that is  $\geq 8\%$ .

Patients with an STS risk score that is  $< 8\%$  will be assigned high risk if frailty indices and/or existing comorbidities not captured by STS are also present. Specifically, assessments of patient's physical performance including a 15-foot (5m) gait speed test, grip strength testing and Katz Index of Independence in Activities of Daily Living will be considered along with surgical comorbidities not addressed in the STS score (including porcelain aorta, pulmonary hypertension, severe mitral regurgitation, moderate-severe tricuspid regurgitation, diabetes, chronic kidney disease, chronic and oxygen dependent lung disease).

#### 5.1.2 Extreme risk classification

Extreme risk classification will be assigned to subjects with severe aortic stenosis symptoms who are deemed unsuitable for conventional aortic valve replacement because of predicted probability of  $\geq 50\%$  mortality, or at risk for a serious irreversible complication by 30 days.

Subjects with an STS risk score that is  $> 8\%$ , aged  $> 90$  years and with a frailty index  $\geq 2$  will automatically qualify for extreme risk classification.

## Clinical Investigation Plan

### 5.2 Subject Screening and Informed Consent

#### 5.2.1 Subject Screening

Potential patients presenting at the study sites will be fully informed about the clinical investigation, following the established Informed Consent process (described in Section 5.2.2). Once a duly dated and signed Informed Consent form is obtained, the clinical investigation-specific screening procedures may begin. All cardiac medications and all medications given for cardiovascular effect may be continued at their prescribed dosages for the screening assessments.

The following assessments are performed as part of the screening process:

1. Demographics (age on consent date, gender, height)
2. Medical History (including previous cardiovascular operations and events, coexisting cardiovascular diseases, clinically significant peripheral vascular disease, previous peripheral vascular operations, other coexisting medical conditions e.g., diabetes, hypertension, kidney and lung disease, endocarditis)
3. Canadian Cardiovascular Society (CCS) Angina Scale Assessment
4. Surgical Risk Assessment tools (STS Risk Score and EuroSCORE II)
5. Forced Expiratory Volume (FEV1) Test, if clinically indicated
6. Physical Exam (including weight, heart rate, blood pressure)
7. Echocardiography to include comprehensive transthoracic or transesophageal 2D echocardiogram, including assessment of aortic valve gradients (mean and peak), areas, indices, degree of regurgitation, cardiac output and cardiac index, left ventricle systolic function (global and segmental)
8. Lab Measurements (including CBC and Platelet count, BUN and creatinine, BNP or ProBNP, and Albumin)
9. 12 Lead Electrocardiogram (ECG)
10. Computed Tomography Scan with Angiography for chest, abdomen and pelvis: aortic root and valve annulus sizing, assessment of suitability of iliofemoral access, and determination of appropriate coaxial angles for optimizing the valve implantation procedure. CT scan performed up to 12 months prior to consent will be acceptable.
11. 3D Transesophageal Echocardiogram (TEE) if CT is contraindicated
12. New York Heart Association (NYHA) Functional Classification
13. Frailty Index Assessment (Katz index of Activities of Daily Living, Grip Strength, 5 meter walk test)
14. Coronary and aortic angiogram (arteriograms of the lower abdominal aorta to the femoral arteries), with runoff if clinically indicated. Coronary and aortic angiogram performed up to 12 months prior to consent will be acceptable.
15. Adverse Event Assessment

Subjects must be screened for clinical investigation eligibility by a member of the study site's clinical investigation team (Principal Investigator and/or Research Coordinator) previously trained to the CIP, and if applicable will be entered into a site-specific screening log.

## Clinical Investigation Plan

In case the subject does not meet all inclusion criteria or meets any of the exclusion criteria, the subject will be considered a screening failure. The Principal Investigator or the delegated clinical investigation personnel will record the screening failure in the hospital records and on a screening log as applicable.

Patients meeting general inclusion criteria and no exclusion criteria will be asked to sign an Informed Consent form if they wish to participate in the clinical investigation. These patients will also be entered into the screening log.

Providing Informed Consent is the first step in the enrollment process however the subject is not fully enrolled in the study until all enrollment steps are complete per protocol (see section 5.4). However, once the patient has provided Informed Consent, study-specific subject data will be collected in the clinical investigation. Screening tests that are specifically study-related and would generally not be considered standard of care in Europe include:

- Frailty Index Assessment (Katz index of Activities of Daily Living, Grip Strength, 5 meter walk test)
- Forced Expiratory Volume Test (if clinically required)
- New York Heart Association (NYHA) Functional Classification
- Canadian Cardiovascular Society (CCS) Angina Scale Assessment

Refer to APPENDIX VII for a description of the tests involved in the Frailty Index Assessment.

Data available in the patient's medical record may be utilized to fulfill screening requirements and testing does not need to be repeated if performed within 60 days prior to Informed Consent. Computed Tomography (CT) scan with angiography and coronary and aortic angiogram (with runoff if clinically indicated) may be performed within 12 months prior to Informed Consent.

Upon initial screening of eligibility of patients by the local Heart Team, subject case reviews will be conducted by an independent SSC to confirm a patient's eligibility to transfemorally receive a Portico™ valve. The SSC will also provide final determination of a subject's risk classification for the study. If a site disagrees with the committee's final decision regarding risk classification the subject will not be eligible for enrollment in the study. If the SSC does not approve the patient, they will be exited from the study as a screen failure.

